**Table 12: Time points for Coagulation, Direct Antiglobulin Test and Microbiology SAD**

Time point	Target	Interval for Analysis
Baseline	Day 1 dose start time	Most recent value prior to first dose
Day 8	Day 8	]Day 1 dose end time, End of study]

**Table 13: Time points for Coagulation MAD**

Time point	Target	Interval for Analysis
Baseline	Day 1 dose start time	Most recent value prior to first dose
Day 8 Pre-dose	Day 8 dose start time	]Day 1 dose end time, Day 8 dose start time[
Day 33	Day 33	[Day 8 dose end time, End of Study]

**Table 14: Time points for Direct Antiglobulin Test and Microbiology MAD**

Time point	Target	Interval for Analysis
Baseline	Day 1 dose start time	Most recent value prior to first dose
Day 33	Day 33	]Day 1 dose end time, End of Study]

**Table 15: Time points for CRP and ESR SAD**

Time point	Target	Interval for Analysis
Baseline	Day 1 dose start time	Most recent value prior to first dose
Day 2	Day 2	[Day 2, Day 3[
Day 8	Day 8	[Day 3, End of Study]

**Table 16: Time points for CRP and ESR MAD**

Time point	Target	Interval for Analysis
Baseline	Day 1 dose start time	Most recent value prior to first dose
Day 15 Pre-dose	Day 15 dose start time	]Day 1 dose end time, Day 15 dose start time[
Day 22 Pre-dose	Day 22 dose start time	]Day 15 dose end time, Day 22 dose start time[
Day 33		[Day 22 dose end time, End of Study]

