8.5 Laboratory Evaluations

Laboratory evaluations will be performed according to the study schedule. For screening purposes, should the screening period require longer than 14 days (eg, CFTR genotype testing required longer than 14 days), safety evaluations (serum chemistries, hematologies, urinalysis, physical exam, vital signs, spirometry) must be re-obtained for confirmation of eligibility and enrollment into the study.

Serum chemistries will include sodium, potassium, chloride, bicarbonate, blood urea nitrogen (BUN), creatinine, glucose, calcium, phosphorus, SGPT/ALT, SGOT/AST, GGT, alkaline phosphatase, bilirubin (total and direct), uric acid, lactic dehydrogenase (LDH), albumin,

total protein, triglycerides, and cholesterol. Creatinine clearance is to be calculated using the Cockcroft-Gault equation adjusted for actual body weight. At screening, tocopherol (Vitamin E) levels will also be measured.

Hematologies will include a complete blood count: Complete blood count (CBC) with absolute differential (hematocrit, hemoglobin, white blood count, segmented neutrophils, bands, lymphocytes, monocytes, eosinophils, basophils, platelet count).

A Direct Antiglobulin Test (DAT) will also be performed at screening and 7 days after last dose.

Erythrocyte sedimentation rate (ESR) and C-reactive protein (CRP) will be measured at baseline, 24 hours post dose, and End of Study Visit for SAD cohorts, and at baseline, prior to doses 4, 7 and 10, and at the End of Treatment Visit for MAD cohorts. Two baseline measurements will be made; one on Day -1, and the other prior to dosing on Day 1.

Urinalysis (by visual inspection and dipstick) will include color and appearance, specific gravity, pH, protein, glucose, occult blood, ketones, bilirubin, leukocyte esterase, nitrite, and urobilinogen. In addition, microscopic analyses will be performed on samples with abnormal dipstick results. Urine microalbumin will be measured at baseline for SAD and MAD cohorts; end of study for SAD cohorts; and prior to dose 10 and end of study for MAD cohorts. Time of void will be recorded for each urine sample collected. At screening, testing for drugs of abuse will also be performed, specifically for amphetamines, methamphetamines, methylenedioxyamphetamine, cocaine, cannabinoids, phencyclidine, opiates, methadone, barbiturates, benzodiazepines, ethyl alcohol. Urine or blood testing for drugs of abuse is permitted.

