## **4. STATISTICAL METHODS**

### **4.1. Sample Size Justification**

This is a Phase 1 safety study designed to evaluate the safety, tolerability and PK of QR-010. The sample size is not based on power calculations. It is chosen based on clinical experience and considered to be adequate to fulfill the objectives of the study.

Approximately 64 subjects will be enrolled in the study, with 8 subjects per cohort (6 QR-010 and 2 placebo), 32 each in the SAD and MAD portions of the study. The exact number of subjects enrolled is dependent on whether any dose levels are to be expanded due to the occurrence of AEs of interest.

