#### 4.2.7.4. Sweat Chloride

**Table 17: Time points for Sweat Chloride MAD**

Time point	Target	Interval for Analysis
Baseline	Day 1 dose start time	Most recent value prior to first dose
Day 26	Day 26	[Day 1 dose end time, Day 26+3 days]
Day 33	Day 33	[Day 26+4 days ; Day 33+ 7 days]
Day 54	Day 54	[Day 33+8 days ; End of Study]

If several assessments are done on the same day, the average of these assessments will be used.

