#### 4.8.2.6. C-Reactive Protein (CRP) (mg/L)

CRP value and change from baseline will be presented descriptively over time, per treatment group.

Graphical representation will be provided (mean change from baseline +95% CI overtime).

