**Table A.2-3: Multiple Ascending Dose Cohorts 5-8, WEEK 2**

Labs	Dose 4		Dose 5		Dose 6		
Study Day	8	9	10	11	12	13	14
In Hours	168	192	216	240	264	288	312
Hematology	X						
Serum Chemistry	X						
Hematology & Chemistry	Dose 4: Pre-dose, 15, 60 minutes, 2 hours post dose						
C-Reactive Protein	X						
Erythrocyte Sedimentation Rate	X						
C-Reactive Protein & Erythrocyte Sedimentation Rate	Dose 4: Pre-dose						
Coagulation and CH50	X						
Urine microalbumin			X				
Urinalysis	X						
	Dose 4: Pre-dose, 60 minutes and 2 hours post dose Dose 10: Urine microalbumin pre-dose						
PK Sampling	Serum: Prior to Dose 4, 5, and 6 Sputum: Prior to Doses 4, 5, and 6						
Serum for PK	X		X		X		
Sputum for PK	X		X		X		
Biomarker Sampling	Dose 4: Pre-dose						
Blood (serum and plasma) for Biomarkers	X						
Sputum for Biomarkers	X						

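### SAP Table 16 has no Day 8 row for MAD CRP and ESR, so the samples before doses 4 and 7 share the Day 15 window and no rule says which is used

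*SAP*

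**What the plan says.** Protocol Section 8.5 schedules MAD CRP and ESR at baseline and then "prior to doses 4, 7 and 10, and at the End of Treatment Visit for MAD cohorts". The SAP repeats this in its own laboratory schedule: Table A.2-3 (Week 2) marks both tests in the Dose 4 column, with the timing given as "Dose 4: Pre-dose". SAP Table 5 places dose 4 on Day 8, dose 7 on Day 15 and dose 10 on Day 22. End of Treatment is Day 33.

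SAP Table 16, which assigns MAD CRP and ESR values to analysis time points, has four rows: baseline, Day 15 pre-dose, Day 22 pre-dose and Day 33. The Day 15 window is "Day 1 dose end time, Day 15 dose start time" and the Day 22 window is "Day 15 dose end time, Day 22 dose start time". There is no Day 8 row.

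The windows feed SAP Section 4.8.2.6, where "CRP value and change from baseline will be presented descriptively over time, per treatment group". Section 4.8.2.7 treats ESR in the same way. Both sections also commit to a graph of mean change from baseline with a 95% confidence interval over time.

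**The concern.** A window table should give each scheduled sample its own time point, or say why it does not. Table 16 does neither for the sample before dose 4. Three other MAD laboratory tables cover tests sampled before dose 4, and each has a Day 8 pre-dose row: hematology and chemistry (Table 9), urinalysis (Table 11) and coagulation (Table 13, "Day 1 dose end time, Day 8 dose start time"). Where the SAP deliberately leaves out assessments, as with post-dose spirometry and repeat glucose values in the mixed models, it gives a reason. It gives none here, so this looks like an omission.

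Two things are at stake. The CRP and ESR time courses would begin at Day 15, although a Day 8 value was collected. And the Day 15 point could mix values taken after six doses with values taken after three, depending on how the programmer handles the shared window and on which subjects lack a Day 15 sample.

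**Working it through.** There is no stated figure to reproduce. The check maps each scheduled sample onto the Table 16 intervals.

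**Inputs**
- Nominal times in hours after dose 1, from the Table A.2 schedules: dose 4 at 168, dose 7 at 336, dose 10 at 504, End of Treatment at 768, End of Study at 1272.
- End of inhalation is taken as 20 minutes (0.33 h) after the start. This is an assumption based on the SAP Section 4.7 statement that a complete administration should take less than about 20 minutes. The result does not depend on it.
- Planned MAD enrolment is 32, from SAP Section 4.1: "32 each in the SAD and MAD portions of the study".

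**Table 16 in hours**
- Day 15 pre-dose: after 0.33 and before 336. Width (336 − 0.33)/24 = 13.99 days.
- Day 22 pre-dose: after 336.33 and before 504.
- Day 33: from 504.33 to End of Study.

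**Mapping**

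| Scheduled sample | Hour | Window under Table 16 | Window with a Day 8 row added |
|---|---|---|---|
| Before dose 4 (Day 8) | just before 168 | Day 15 pre-dose | Day 8 pre-dose |
| Before dose 7 (Day 15) | just before 336 | Day 15 pre-dose | Day 15 pre-dose |
| Before dose 10 (Day 22) | just before 504 | Day 22 pre-dose | Day 22 pre-dose |
| End of Treatment (Day 33) | 768 | Day 33 | Day 33 |

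Four scheduled samples go into three windows. With the added row the match is one to one.

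**Size**
- Scheduled post-baseline values per marker: 32 × 4 = 128.
- Values without a time point of their own: 32 × 1 = 32, and 32/128 = 25%.
- If a subject has no Day 15 sample, the value that fills that point was taken (336 − 168)/24 = 7 days before target, after three doses instead of six.

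**Is there a rule for two values in one window?** The only averaging rule among the window tables is attached to sweat chloride ("If several assessments are done on the same day, the average of these assessments will be used"). It covers same-day repeats, so it would not apply to samples a week apart even if it were extended to CRP and ESR. SAP Section 4.10.2.1 uses all post-baseline assessments for shift tables, but CRP and ESR are not in the hematology or chemistry lists (Sections 4.10.2.2 and 4.10.2.3), and a shift table would not restore a Day 8 time point anyway. The post hoc SAP does not deal with either marker.

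**The case against.** The strongest reply is that little follows from the gap, and most of that reply stands.

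- A reader might infer that the Day 8 data are lost. The documents do not support that. SAP Section 4.10.2.1 provides for listings of laboratory data, and the CRP and ESR windows sit under the SAP's laboratory heading (4.2.7.3). The raw values remain; only their place in the by-time summaries and graphs is affected.
- A reader might infer that the earliest on-treatment reading of inflammation disappears. That goes too far. Protocol Section 7.4.5 takes blood and sputum for inflammatory biomarkers on Day 4, and white cell counts with differentials are taken from Day 1 and have their own windows in Table 9. What lacks a row is the first on-treatment CRP and ESR value.
- Table 16 gives the Day 15 dose start as the target. If the programmer takes the value closest to target, the Day 15 sample is used whenever it exists, and only subjects without one are mislabelled. That is a sensible reading, but the SAP does not state it. Averaging the two values or keeping both would be equally consistent with the text.
- CRP and ESR are not among the exploratory efficacy evaluations named in Protocol Section 13.10. The SAP adds them and summarises them descriptively.

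None of this supplies the missing row or the missing rule.

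**Conclusion.** The point holds, as a minor one. SAP Table 16 disagrees with the protocol and with the SAP's own sampling schedule. Applied as written, it puts two scheduled samples in Day 15 and gives the Day 8 sample no time point. Which value represents Day 15 is undetermined when both exist. When the Day 15 sample is missing, a Day 8 value is reported under the Day 15 label.

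The size is one of four scheduled post-baseline samples for each marker, about 32 values each. This assumes the planned MAD enrolment of 32 and complete sampling. It is not a ceiling: if all four MAD cohorts were expanded by four subjects (Protocol Sections 4.3 and 5.2), the count would be 32 + 4 × 4 = 48. Withdrawals before dose 4 would lower it. The 25% is the share of scheduled samples without their own row, not a share of data lost.

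The consequence is confined to descriptive summaries and graphs. The mixed models and MCPMod analyses in SAP Section 4.8.2 cover ppFEV1, glucose, CFQ-R RSS and weight (for glucose, CFQ-R RSS and weight as well as ppFEV1, placebo differences are estimated), and none uses CRP or ESR. Anyone inferring that an efficacy test or a dose-escalation decision is affected would find no support in the documents.

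**What to change.** In SAP Table 16:

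1. Add a Day 8 pre-dose row, target Day 8 dose start time, with the open interval already used in Table 13: "Day 1 dose end time, Day 8 dose start time".
2. Move the lower bound of the Day 15 pre-dose window from the end of the Day 1 dose to the end of the Day 8 dose, leaving its upper bound at the start of the Day 15 dose.
3. State that when several values fall in one window, the one closest to the target is used. Without this, unscheduled repeats stay ambiguous even after the row is added.

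The cost is one new row, one changed bound and one sentence, plus a rerun of the MAD CRP and ESR summaries and graphs if they have been programmed. No new data are needed and no inferential result changes. Subjects without a Day 15 sample will now be counted as missing at Day 15, so the number at that point may fall slightly. That is the correct description of the data.

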#### 4.2.7.4. Sweat Chloride

**Table 17: Time points for Sweat Chloride MAD**

Time point	Target	Interval for Analysis
Baseline	Day 1 dose start time	Most recent value prior to first dose
Day 26	Day 26	[Day 1 dose end time, Day 26+3 days]
Day 33	Day 33	[Day 26+4 days ; Day 33+ 7 days]
Day 54	Day 54	[Day 33+8 days ; End of Study]

If several assessments are done on the same day, the average of these assessments will be used.

#### 4.2.7.5. Vital Signs and Weight

**Table 18: Time points for Vital Signs SAD**

Time point	Target	Interval for Analysis
Baseline	Day 1 dose start time	Most recent value prior to first dose
Day 1 1min Post-dose	Day 1 dose end time+1min	]Day 1 dose end time, Day 1 dose end time+5min]
Day 1 10 min Post-dose	Day 1 dose end time+10min	]Day 1 dose end time+5min, Day 1 dose end time+20min]
Day 1 30min Post-dose	Day 1 dose end time+30min	]Day 1 dose end time+20min, Day 1 dose end time+45min]
Day 1 60min Post-dose	Day 1 dose end time+60min	]Day 1 dose end time+45min, Day 1 dose end time+90min]
Day 1 2hrs Post-dose	Day 1 dose end time+2h	]Day 1 dose end time+90min, Day 1 dose end time+3h]
Day 1 4hrs Post-dose	Day 1 dose end time+4h	]Day 1 dose end time+3h, Day 1 dose end time+8h]
Day 1 12hrs Post-dose	Day 1 dose end time+12h	]Day 1 dose end time+8h, Day 2[
Day 2	Day 2	[Day 2, Day 3[
Day 3	Day 3	[Day 3, Day 4[
Day 4	Day 4	[Day 4, Day 7[
Day 8	Day 8	[Day 7, End of Study]

**Table 19: Time points for Weight SAD**

Time point	Target	Interval for Analysis
Baseline	Day 1 dose start time	Most recent value prior to first dose
Day 8	Day 8	]Day 1 dose end time, End of study]

**Table 20: Time points for Vital Signs MAD**

Time point	Target	Interval for Analysis
Baseline	Day 1 dose start time	Most recent value prior to first dose
Day 1 1min Post-dose	Day 1 dose end time+1min	]Day 1 dose end time, Day 1 dose end time+5min]
Day 1 10 min Post-dose	Day 1 dose end time+10min	]Day 1 dose end time+5min, Day 1 dose end time+20min]
Day 1 30min Post-dose	Day 1 dose end time+30min	]Day 1 dose end time+20min, Day 1 dose end time+45min]
Day 1 60min Post-dose	Day 1 dose end time+60min	]Day 1 dose end time+45min, Day 1 dose end time+90min]
Day 1 2hrs Post-dose	Day 1 dose end time+2h	]Day 1 dose end time+90min, Day 1 dose end time+3h]
Day 1 4hrs Post-dose	Day 1 dose end time+4h	]Day 1 dose end time+3h, Day 1 dose end time+8h]
Day 1 12hrs Post-dose	Day 1 dose end time+12h	]Day 1 dose end time+8h, Day 3[
Day 3 Pre-dose	Day 3 dose start time	[Day 3, Day 3 dose start time[
Day 3 1min Post-dose	Day 3 dose end time+1min	]Day 3 dose end time, Day 3 dose end time+5min]
Day 3 10 min Post-dose	Day 3 dose end time+10min	]Day 3 dose end time+5min, Day 3 dose end time+20min]
Day 3 30min Post-dose	Day 3 dose end time+30min	]Day 3 dose end time+20min, Day 3 dose end time+45min]
Day 3 60min Post-dose	Day 3 dose end time+60min	]Day 3 dose end time+45min, Day 3 dose end time+90min]
Day 3 2hrs Post-dose	Day 3 dose end time+2h	]Day 3 dose end time+90min, Day 3 dose end time+3h]
Day 3 4hrs Post-dose	Day 3 dose end time+4h	]Day 3 dose end time+3h, Day 3 dose end time+8h]
Day 3 12hrs Post-dose	Day 3 dose end time+12h	]Day 3 dose end time+8h, Day 4[
Day 4	Day 4	[Day 4, Day 5[
Day 5 Pre-dose	Day 5 dose start time	[Day 5, Day 5 dose start time[
Day 5 1min Post-dose	Day 5 dose end time+1min	]Day 5 dose end time, Day 5 dose end time+5min]
Day 5 10 min Post-dose	Day 5 dose end time+10min	]Day 5 dose end time+5min, Day 5 dose end time+20min]
Day 5 30min Post-dose	Day 5 dose end time+30min	]Day 5 dose end time+20min, Day 5 dose end time+45min]
Day 5 60min Post-dose	Day 5 dose end time+60min	]Day 5 dose end time+45min, Day 5 dose end time+90min]
Day 5 2hrs Post-dose	Day 5 dose end time+2h	]Day 5 dose end time+90min, Day 7[
Day 8 Pre-dose	Day 8 dose start time	[Day 7, Day 8 dose start time[
Day 8 1min Post-dose	Day 8 dose end time+1min	]Day 8 dose end time, Day 8 dose end time+5min]
Day 8 10 min Post-dose	Day 8 dose end time+10min	]Day 8 dose end time+5min, Day 8 dose end time+20min]
Day 8 30min Post-dose	Day 8 dose end time+30min	]Day 8 dose end time+20min, Day 8 dose end time+45min]
Day 8 60min Post-dose	Day 8 dose end time+60min	]Day 8 dose end time+45min, Day 8 dose end time+90min]
Day 8 2hrs Post-dose	Day 8 dose end time+2h	]Day 8 dose end time+90min, Day 9[
Day 10 Pre-dose	Day 10 dose start time	[Day 9, Day 10 dose start time[

Day 12 Pre-dose	Day 12 dose start time	]Day 10 dose end time, Day 12 dose start time[
Day 15 Pre-dose	Day 15 dose start time	]Day 12 dose end time, Day 15 dose start time[
Day 15 1min Post-dose	Day 15 dose end time+1min	]Day 15 dose end time, Day 15 dose end time+5min]
Day 15 10 min Post-dose	Day 15 dose end time+10min	]Day 15 dose end time+5min, Day 15 dose end time+20min]
Day 15 30min Post-dose	Day 15 dose end time+30min	]Day 15 dose end time+20min, Day 15 dose end time+45min]
Day 15 60min Post-dose	Day 15 dose end time+60min	]Day 15 dose end time+45min, Day 15 dose end time+90min]
Day 15 2hrs Post-dose	Day 15 dose end time+2h	]Day 15 dose end time+90min, Day 16[
Day 17 Pre-dose	Day 17 dose start time	[Day 16, Day 17 dose start time[
Day 19 Pre-dose	Day 19 dose start time	]Day 17 dose end time, Day 19 dose start time[
Day 22 Pre-dose	Day 22 dose start time	]Day 19 dose end time, Day 22 dose start time[
Day 22 1min Post-dose	Day 22 dose end time+1min	]Day 22 dose end time, Day 22 dose end time+5min]
Day 22 10 min Post-dose	Day 22 dose end time+10min	]Day 22 dose end time+5min, Day 22 dose end time+20min]
Day 22 30min Post-dose	Day 22 dose end time+30min	]Day 22 dose end time+20min, Day 22 dose end time+45min]
Day 22 60min Post-dose	Day 22 dose end time+60min	]Day 22 dose end time+45min, Day 22 dose end time+90min]
Day 22 2hrs Post-dose	Day 22 dose end time+2h	]Day 22 dose end time+90min, Day 23 [
Day 24 Pre-dose	Day 24 dose start time	[Day 23, Day 24 dose start time[
Day 26 Pre-dose	Day 26 dose start time	]Day 24 dose end time, Day 26 dose start time[
Day 26 1min Post-dose	Day 26 dose end time+1min	]Day 26 dose end time, Day 26 dose end time+5min]
Day 26 10 min Post-dose	Day 26 dose end time+10min	]Day 26 dose end time+5min, Day 26 dose end time+20min]
Day 26 30min Post-dose	Day 26 dose end time+30min	]Day 26 dose end time+20min, Day 26 dose end time+45min]
Day 26 60min Post-dose	Day 26 dose end time+60min	]Day 26 dose end time+45min, Day 26 dose end time+90min]
Day 26 2hrs Post-dose	Day 26 dose end time+2h	]Day 26 dose end time+90min, Day 26+3days ]
Day 33	Day 33	[Day 26+4 days ; Day 33+ 7 days]
Day 54	Day 54	]Day 33+8 days ; End of Study]

---

**Table 21: Time points for Weight MAD**

Time point	Target	Interval for Analysis
Baseline	Day 1 dose start time	Most recent value prior to first dose
Day 8	Day 8	]Day 1 dose end time, Day 8 + 3 days]
Day 15	Day 15	[Day 8 +4days, Day 15+3 days]
Day 22	Day 22	[Day 15 +4days, Day 22+2 days]
Day 26	Day 26	[Day 22 +3days, Day 26+3 days]
Day 33	Day 33	[Day 26+4 days ; Day 33+ 7 days]
Day 54	Day 54	[Day 33+8 days ; End of Study]

#### 4.2.7.6. Cystic Fibrosis Questionnaire Revised (CFQ-R)

**Table 22: Time points for CFQ-R MAD**

Time point	Target	Interval for Analysis
Baseline	Day 1 dose start time	Most recent value prior to first dose
Day 15	Day 15	[Day 1 dose end time, Day 15+9 days]
Day 33	Day 33	[Day 15+10 days ; Day 33+ 7 days]
Day 54	Day 54	[Day 33+8 days ; End of Study]

#### 4.2.7.7. Electrocardiogram (ECG)

**Table 23: Time points for ECG SAD**

Time point	Target	Interval for Analysis
Baseline	Day 1 dose start time	Most recent value prior to first dose
Day 8	Day 8	]Day 1 dose end time, End of study]

**Table 24: Time points for ECG MAD**

Time point	Target	Interval for Analysis
Baseline	Day 1 dose start time	Most recent value prior to first dose
Day 33	Day 33	]Day 1 dose end time, End of Study]

#### 4.2.8. Descriptive Statistics

Tabulations will be produced for appropriate demographic, baseline, efficacy, pharmacokinetic and safety parameters.

For categorical variables, summary tabulations of the number and percentage within each category (with a category for missing data) of the parameter will be presented.

For continuous variables, the mean, standard deviation, median, first quartile (Q1), third quartile (Q3), minimum and maximum values will be presented.

For PK parameters percentage of coefficient of variation will be added.

#### 4.2.9. Dictionaries

Adverse events and Medical history are to be coded using the Medical Dictionary for Regulatory Activities (MedDRA) using the latest version available at the time of the lock for the SAD. The same version for the SAD and the MAD should be used.

Concomitant medications are to be coded using the WHODrug dictionary using the latest version available at the time of the lock.

#### 4.2.10. Computing Environment

Statistical analyses will be performed using SAS statistical software (Version 9.2 or higher).

R software version 3.3.2 or higher will be also used for modelling and some graphics.

Cytel Proc MCPMod 1.1, East 6.3 PROCs for SAS will be used modelling

PK parameters will be generated using validated software (Phoenix WinNonlin® Version 6.3, or higher).

### 4.3. Interim Analyses

Safety will be assessed prior to each dose escalation by the DSMC.

For development purposes data analyses may be performed during the study.

### 4.4. Subject Disposition

The number of subjects enrolled, number of screened failure will be tabulated.

The number of subjects in each population will be presented.

The number and percentage of subjects randomized, treated, completed treatment/discontinued from treatment (reasons), completed study and discontinued from the study and reasons will be presented for the safety population. The enrollment by geographic region (North America and Europe) region and by site will be tabulated.

Display will be presented by dose and total. Display may be repeated with the exploratory analysis population if exploratory analysis and safety populations differ.

A by-subject listing of study disposition (informed consent date, first dose, completion status, last treatment date, and last study date, including the reason for premature treatment/study withdrawal, if applicable) will be presented.

